Infant Development. Recent reviews have noted the need to consider the longer-term impact of in utero exposure to opioid maintenance on children, for which there is currently a dearth of research.¹⁴ The 6-month and 12-month versions of the Ages and Stages Questionnaire, third edition (ASQ-3)⁷¹ will be used to screen infants for developmental issues. The ASQ-3 is a validated, parent-administered screen used throughout the world⁷¹⁻⁷³ and deemed appropriate for assessing infants exposed to opioids in utero.¹³ An association between FHRV and development has been found in a number of studies.⁷⁴⁻⁷⁶ Furthermore, a recent study found that the relationship between maternal depression and neonatal neurobehavioral immaturity was mediated by FHRV.⁷⁷ It is thus predicted that fetal behavior, as measured by FHRV, will be a significant predictor of scoring below the ASQ-3 cut-off. Research has also found a relationship between NOWS severity and infant development^{78, 79} and it is, thus, predicted that NOWS-related outcomes will predict ASQ-3 scores.

NOWS-related outcomes. Approximately 50% of infants born to women on opioid maintenance treatment will experience NAS/NOWS.¹⁴ Factors that can impact NOWS include maternal polysubstance use,^{32, 80} EGA at delivery and birth weight,^{81, 82} and nonpharmacological treatment approaches.⁸³ Controlling for these factors as needed, the mechanisms by which BUP-XR, relative to BUP-SL, may impact NOWS-related outcomes will be evaluated. It has been hypothesized that the daily peak-to-trough fluctuation associated with opioid maintenance treatment results in the fetus experiencing withdrawal, which increases the incidence and severity of NAS/NOWS.⁷⁰ Consistent with this hypothesis, a retrospective study evaluating NAS/NOWS incidence in infants born to mothers maintained on a split-dosing schedule of methadone reported a lower incidence of NAS/NOWS (29%)⁷⁰ relative to the 50% typically associated with methadone maintenance.^{14, 83} It is thus predicted that fetal behavior, as measured by FHRV, will be a significant predictor of NOWS outcomes.

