
7.2.1.2 *Drug and Alcohol Abstinence*

Drug and alcohol abstinence during pregnancy and postpartum are secondary outcomes and will be assessed in a fashion similar to the assessment of illicit opioid abstinence, but rather than being restricted to illicit opioid use, will include alcohol and other drugs of abuse. Missing urine samples will be imputed as positive.

7.2.1.3 *The Opioid Craving Scale*

Craving will be assessed with the Opioid Craving Scale, which was utilized in CTN-0030 and shown to have predictive validity.¹¹² The total score is calculated by averaging the scores from three visual analogue scales which assess craving, cue-induced craving, and likelihood of using.

7.2.1.4 *Adequacy of Prenatal Care Utilization*

Kotelchuck's Adequacy of Prenatal Care Utilization (APNCU) index,¹¹³ which is a well-established index,¹¹⁴ will be used to assess the adequacy of prenatal care. The APNCU includes two indices that are combined to obtain a total score. One index is the timing of prenatal care initiation scored in 4 categories [EGA months: 1) 1 and 2; 2) 3 and 4; 3) 5 and 6; and 4) 7 to 9]. The second is the ratio of observed to expected visits based on the length of time between the first prenatal care visit and delivery, scored in 4 categories: 1) Inadequate (received less than 50% of expected visits); 2) Intermediate (50%-79%); 3) Adequate (80%-109%); 4) Adequate Plus (110% or more). The information for the APNCU will be derived from either medical records or the birth certificate. The % of expected visits attended prior to study randomization will be included as a baseline covariate in analyses.

7.2.1.5 *The Short Opiate Withdrawal Scale (SOWS)-Gossop*

The SOWS-Gossop¹¹⁵ will be used to measure opioid withdrawal symptoms. The SOWS-Gossop, which is a self-administered scale that includes 10 items, rated on a scale of 0 (none) to 3 (severe), is a validated instrument with good reliability.¹¹⁶ It will be completed following the schedule in **Table 3**.

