7.3.9 Infant Sedation

The limited data available has revealed low levels of BUP and BUP metabolites in the breastmilk of BUP-maintained women¹¹⁹ and breastfeeding is recommended for stable BUP-maintained women.¹²⁰ However, more data on potential infant exposure through breastfeeding is needed for BUP-maintained women and data on BUP/NX-maintained women⁶⁷ and BUP-XR-maintained women is lacking. While no adverse reactions are expected in breastfed infants in the present study, a theoretically possible and concerning adverse reaction, infant sedation, will be assessed via mother-report as outlined in **Table 3**. The infant sedation assessment will be completed by participants who are feeding their infants with breastmilk and/or formula and will assess for signs of infant sedation (e.g., not waking for feeding, difficulty breathing, etc.). In addition, if an infant sedation assessment in a breastfed infant meets the criteria of an SAE, it will be collected as an SAE, as all infant SAEs occurring in breastfed infants will be collected.

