Infant Sedation: Infant sedation will be assessed via mother-report as outlined in **Table 3**. The infant sedation assessment will be completed by participants who are feeding their infants with breastmilk and/or formula and will assess for signs of infant sedation (e.g., not waking for feeding, difficulty breathing, etc.).

Bayley™-4. The Bayley™-4¹⁰² includes cognitive, language, fine motor, and gross motor subscales.

Child Behavior Checklist (CBCL). The CBCL¹⁷⁴ is administered to caregivers and includes items that describe behavioral, emotional, and social problems that characterize preschool children.

Events related to withdrawal symptoms will be captured on the SOWS-Gossop and will not be duplicate-reported on an AE form. However, precipitated withdrawal during study medication induction will be reported as an AE. Events captured on study specific forms (e.g., HADS) will not be recorded separately as an AE, unless they meet the SAE definition. Any of these events that meet the definition of an SAE, during the reporting periods described below, will be reported on the AE/SAE form set.

Adverse Events and Serious Adverse Events:

For the purpose of this study and if not described above, these events are required to be reported as an AE/SAE:

- All deaths that occur in either the Mother or the Infant (SAE)
- Congenital anomaly observed (SAE)
- Other infant SAEs that occur in breastfed infants
- All maternal AEs/SAEs while on study, except as noted below in “Events that do not require AE/SAE reporting”
- Maternal hospital re-admission within 6 weeks of delivery (SAE)
- Any ICU admission during the Labor and delivery admission (SAE)
- An opioid overdose resulting in naloxone rescue (SAE)

Events that do not require AE/SAE reporting:

- Hospitalization for Labor and Delivery, unless the hospitalization results in an ICU admission
- Prolongation of the hospital stay for a delivery (unless greater than 4 days for vaginal delivery or 7 days for C-section delivery)
- Admission to a hospital for elective surgery or pre-scheduled diagnostic tests
- Opioid overdose, unless resulting in naloxone rescue, hospitalization, or death
- Infant AEs and SAEs, except infant deaths, congenital anomalies in all infants, , and other infant SAEs in breastfed infants

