16.0 APPENDIX A: ADVERSE EVENT REPORTING AND PROCEDURES

Each participating site's Principal Investigator is responsible for study oversight, including ensuring human research subject protection by designating appropriately qualified and trained study personnel to assess, report, and monitor adverse events.

Definition of Adverse Events and Serious Adverse Events

An **adverse event** (AE) is any untoward medical occurrence in humans, whether or not considered study medication related which occurs during the conduct of a clinical trial. Any change from baseline in clinical status, ECGs, lab results, x-rays, physical examinations, etc., that is considered clinically significant by the study medical clinician are considered AEs.

Suspected adverse reaction is any adverse event for which there is a reasonable possibility that the study medication caused the adverse event. A reasonable possibility implies that there is evidence that the study medication caused the event.

Adverse reaction is any adverse event caused by the study medication.

An **adverse event, suspected adverse reaction, or adverse reaction** is considered "**serious**" (i.e., a serious adverse event, serious suspected adverse reaction or serious adverse reaction) if, in the view of either the study medical clinician or sponsor, it:

1. Results in death: A death occurring during the study or which comes to the attention of the study staff during the protocol-defined follow-up period, whether or not considered caused by the study medication, must be reported.
2. Is life-threatening: Life-threatening means that the study participant was, in the opinion of the medical clinician or sponsor, at immediate risk of death from the reaction as it occurred and required immediate intervention.
3. Requires inpatient hospitalization or prolongation of existing hospitalization.
4. Results in persistent or significant incapacity or substantial disruption of the ability to conduct normal life functions.
5. Is a congenital abnormality or birth defect.
6. Is an important medical event that may not result in one of the above outcomes, but may jeopardize the health of the study participant or require medical or surgical intervention to prevent one of the outcomes listed in the above definition of serious event.

Definition of Expectedness

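### Infant SAE reporting does not exempt NOWS, so a NOWS-prolonged newborn stay is a reportable SAE if the infant is breastfed and exempt if formula-fed

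*Combined protocol and SAP*

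**What the plan says.** Section 11.17.2 lists the events that must be reported. For infants these are deaths, congenital anomalies and "Other infant SAEs that occur in breastfed infants". The companion list of events that need no reporting contains "Infant AEs and SAEs, except infant deaths, congenital anomalies in all infants, , and other infant SAEs in breastfed infants". Section 7.3.9 gives the same rule for sedation events, "as all infant SAEs occurring in breastfed infants will be collected", and section 10.3.4.1 repeats it for the analysis.

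Appendix A (section 16.0) makes an event serious if it "Requires inpatient hospitalization or prolongation of existing hospitalization"; section 17.8 has the same criterion. The hospitalization exceptions in 11.17.2 and 17.8 cover labor and delivery, a prolonged delivery stay up to 4 days (vaginal) or 7 days (C-section), and elective or pre-scheduled admissions. NOWS is not among them.

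Two other clauses in 11.17.2 limit duplicate reporting. One says: "Events related to withdrawal symptoms will be captured on the SOWS-Gossop and will not be duplicate-reported on an AE form". The other says that events captured on study forms "will not be recorded separately as an AE, unless they meet the SAE definition".

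NOWS is meanwhile an outcome in every infant. Days of opioid treatment is the key secondary outcome (7.1.2.1). Use of opioid medication, length of stay, adjunct medication, peak score and ICD-10 code are secondary outcomes (7.2.2.1).

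**The concern.** The same clinical event is handled differently according to how the infant is fed. In a breastfed infant, a NOWS stay that counts as prolonged enters the SAE system. In a formula-fed infant it does not. The duplicate count is therefore selected on feeding, for an event already recorded without selection.

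Feeding is decided after randomization. In the BUP-XR arm, breastfeeding goes with weekly injections and not breastfeeding generally with monthly ones (3.4, 9.3). The BUP-SL arm has no such link, so breastfeeding could differ between arms for reasons unrelated to harm. Section 10.3.4.1 presents events by arm and plans no denominator by feeding status.

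Sections 7.3.9 and 4.4.2 also point to different mechanisms. In 7.3.9 the concern in breastfed infants is exposure through milk, with sedation as the example. In 4.4.2 NOWS is attributed to exposure in utero. Reporting NOWS under the breastfed-infant rule mixes the two in any infant SAE total. Each report also brings entry within 24 hours (Appendix A), medical-monitor review within one business day (11.17.3), and notification of five roles with source documents within two weeks (17.8).

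**Working it through.** **Does any clause already exempt NOWS?**

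- *Withdrawal-symptom clause.* It is tied to the SOWS-Gossop, which section 7.2.1.5 describes as follows: "which is a self-administered scale that includes 10 items". A newborn cannot complete it, so the clause covers the mother's withdrawal only.
- *Study-form clause.* It lapses once the event meets the SAE definition.
- *Delivery-stay exception.* It is worded by mode of delivery. Even if it were read to cover the infant, it ends after 4 or 7 days. Section 4.1.1 cites a mean NAS/NOWS stay of 16.9 days (2012).
- *Delivery-hospital criterion.* Participants must plan to deliver where infants are not sent home on opioids for NOWS (4.3.4, 6.4.2.1). Opioid treatment is thus expected to be given in hospital, and opioid-treated NOWS is the form most likely to prolong a stay.

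None of these exempts it.

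**How many reports?** The documents state no expected infant SAE count, so there is no figure to reproduce.

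Inputs from the documents:
- N = about 200 mothers with single-fetus pregnancies (6.2, 6.4.2.1), hence at most about 200 infants.
- P(NOWS) = 0.50: "Approximately 50% of infants born to women on opioid maintenance treatment will experience NAS/NOWS" (4.4.2).

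Assumptions, because the documents give no values:
- b, the proportion breastfed: 0.20 to 0.80.
- h, the proportion of NOWS that is serious: 0.30 to 1.00.
- o, the rate of other SAEs in breastfed infants: 0.05 to 0.30.
- Breastfeeding and NOWS are independent.

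Reports = N × 0.50 × b × h:

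| b | h | Reports, N = 200 |
|---|---|---|
| 0.20 | 0.30 | 6 |
| 0.50 | 0.50 | 25 |
| 0.50 | 1.00 | 50 |
| 0.80 | 1.00 | 80 |

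With N = 176, the size section 10.4.2 calls adequate, the range is about 5 to 70.

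**What share of breastfed-infant SAEs would be NOWS?** Share = 0.5h / (0.5h + o):

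| h | o | Share |
|---|---|---|
| 0.5 to 1.0 | 0.05 to 0.10 | 71% to 91% |
| 0.5 to 1.0 | 0.20 | 56% to 71% |
| 0.3 | 0.20 to 0.30 | 33% to 43% |

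**Can feeding alone move the arm comparison?** Take h = 1 and 100 infants per arm; all rates other than 50% NOWS are illustrative.

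- Equal NOWS, unequal feeding: 0.50 × 0.60 = 30 per 100 against 0.50 × 0.40 = 20 per 100, with no difference in NOWS.
- Unequal NOWS, unequal feeding: 0.385 × 0.65 = 25 per 100 against 0.50 × 0.50 = 25 per 100. A real NOWS difference disappears.

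**Would exempting NOWS be enough?** No. If other SAEs run at 10% of breastfed infants in both arms, 60% against 40% breastfed still gives 0.10 × 60 = 6 against 0.10 × 40 = 4 reportable events per 100 infants. Dividing by breastfed infants gives 6/60 = 4/40 = 10% in each arm. The denominator has to change as well.

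**The case against.** A reader might infer that NOWS reports will swamp the infant SAE tables. The documents do not support that. It depends on three rates they do not give, and the assumed ranges put the NOWS share anywhere from 33% to 91%. The 50% incidence refers to opioid maintenance generally, section 4.1.1 says severity is lower with buprenorphine than with methadone, and section 4.3.4 requires rooming-in, citing less drug treatment and shorter stays.

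Nor is every NOWS case an SAE. Appendix A leaves seriousness to the view of the medical clinician or sponsor. Hospitals set minimum observation days for exposed infants (Table 2), so an observation-only stay need not be a prolongation. It would also be wrong to say that the key efficacy outcome itself becomes an SAE: that outcome is days of opioid treatment, which overlaps with a serious NOWS event but is not the same thing.

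A signal of exposure through milk would not be buried. Infant events are summarized by preferred term, so NOWS would have its own row, and infant sedation has a separate weekly assessment in breastmilk- and formula-fed infants (7.3.9, Table 3). Section 10.3.4.1 offers only an optional comparison by event type and no test of a pooled infant SAE rate. Expedited reporting is for events that are serious, related and unexpected (11.17.2), and section 17.7 already names NOWS as a known risk. Over-inclusive reporting is also defensible in the first trial of BUP-XR in pregnant women.

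All of this stands and limits the size of the point. It does not supply the missing exemption or remove the dependence on feeding.

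**Conclusion.** The reporting gap is established by the text alone. NOWS that prolongs a newborn's stay is reportable in breastfed infants and exempt in formula-fed infants. Counts of NOWS SAEs and of infants with any SAE, by arm, would then reflect breastfeeding as well as harm.

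The size is uncertain: about 6 to 80 reports, or 25 to 50 at 50% breastfed and 50-100% of NOWS serious. These figures rest on the assumed b and h, on the 50% incidence applying to this trial, and on independence. Table 2 lists in-hospital breastfeeding as a covariate for infant outcomes, so independence is doubtful. If breastfed infants have less or milder NOWS, the counts fall.

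NOWS can dominate the infant SAE total but need not. Other preferred-term rows stay readable, deaths and anomalies do not depend on feeding, and no primary or key secondary estimate, test or error rate changes. This is an inexpensive improvement to safety reporting and does not threaten the trial's conclusions.

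**What to change.** - **11.17.2 and 17.8:** state that an infant hospital stay, prolonged stay or drug treatment for NOWS is captured as an outcome and is not reported as an SAE, unless it involves death or meets a seriousness criterion other than hospitalization. Add a cross-reference in 7.3.9, where the rule covers all infant SAEs.
- **Definition:** say what breastfed means for this rule and at what time it is judged. Sections 7.3.9, 10.3.4.1 and 11.17.2 do not.
- **10.3.4.1:** show NOWS for all infants by arm on a separate line outside the infant SAE total. Give the breastfed-only infant SAEs by arm with the number of breastfed infants as denominator. Label that rate descriptive, because it conditions on a post-randomization behaviour. Keep deaths and congenital anomalies on the all-infant denominator.

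The cost is protocol and CRF-guideline wording plus one table shell. In-hospital breastfeeding is already a planned covariate (Table 2), and reporting workload falls. The downside is that the DSMB would see NOWS stays through outcome data, which section 17.3 says it already reviews, and no longer through the SAE listing.

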11.17.3 Medical Monitor

The CCC Safety Monitor/Medical Monitor is responsible for reviewing all adverse events and serious adverse events reported. All SAEs will be reviewed within one business day of being reported in Advantage eClinical. The Medical Monitor will also indicate concurrence or not with the details of the report provided by the site PI. Where further information is needed the Safety Monitor/Medical monitor will discuss the event with the site. Reviews of SAEs will be conducted in the Advantage eClinical data system and will be a part of the safety database. All AEs are reviewed on a regular basis to observe trends or unusual events. The CCC Safety Monitor/Medical Monitor will in turn report events to the sponsor and regulatory authorities if the event meets the definition of an expedited event. Reports will be generated and presented for DSMB meetings.

Standard definitions for adverse events and serious adverse events, their identification, characterization regarding severity and relationship to therapy and processing are described in Appendix A.

11.17.4 Known Potential Toxicities of Study Medication/Intervention

Refer to the investigator's brochure for CAM2038, and package inserts for buprenorphine, and buprenorphine/naloxone.

11.18 Training Requirements

A comprehensive Training Plan will be developed to incorporate general training, study-specific training, mechanisms for competency assessment as well as a detailed description of training, supervision, and fidelity monitoring procedures. The Investigative Team is responsible for the development of a comprehensive Training Plan, instructional material, and delivery of the training, with the team comprised of the Lead Node, CCC, DSC, as well as other participating nodes and subject matter experts, as applicable.

The CTN-0080 study staff will be trained as specified in the study Training Plan. Training will include Human Subjects Protection and GCP as well as protocol-specific training on assessments, medication management for pharmacological studies, study interventions, safety and safety event reporting, study visits and procedures, data management, quality assurance, laboratory procedures, etc. The Lead Node is primarily responsible for development and delivery of study-specific training related to the study intervention(s) and procedures. The CCC is responsible for the development and delivery of non-intervention training, including regulatory and laboratory procedures, safety and safety event reporting, quality assurance and monitoring, etc. The DSC is responsible for training related to data management, the electronic data capture system, and good data management practices. Other parties will contribute as needed based on the subject matter and material to be covered. The various sub-teams will collaborate to deliver quality instructional material designed to prepare research staff to fully perform study procedures based on the assigned research roles and responsibilities.

In addition to general and study-specific training, the Training Plan will include a description of the delivery methods to be used for each training module (e.g., via self-study, online, webcast, or teleconference). Study staff is required to complete institutionally-required training per their research site, IRB, and authorities with regulatory oversight. Tracking of training completion for individual staff as prescribed for assigned study role(s) will be documented, endorsed by the site PI and the Lead Node, and audited by the CCC. As changes occur in the prescribed training, the Training Plan and training documentation tracking forms will be amended to reflect these adjustments.

12.0 DATA MANAGEMENT AND PROCEDURES

12.1 Design and Development

This protocol will utilize a centralized Data and Statistics Center (DSC) for participant data. The DSC will be responsible for the development of the CRFs, development and validation of the clinical study database, ensuring data integrity, and training site and participating node staff on applicable data management procedures. Ideally, a web-based distributed data entry model will be implemented. This system will be developed to ensure that guidelines and regulations surrounding the use of computerized systems used in clinical trials are upheld. The remainder of this section provides an overview of the data management plan associated with this protocol.

12.1.1 Site Responsibilities

The data management responsibilities of each individual site will be specified by the Lead Node and the DSC.

12.1.2 Data Center Responsibilities

The DSC will: 1) develop and apply a data management plan and will conduct data management activities in accordance with that plan; 2) provide final guided source documents and eCRFs for the collection of all participant data required by the study; 3) develop data dictionaries for each eCRF that will comprehensively define each data element; 4) conduct ongoing data monitoring activities on study data from all participating sites; 5) monitor any preliminary analysis data cleaning activities as needed, and 6) rigorously monitor final study data cleaning.

